For hypotheses I, II and IV, moderator analyses involve inclusion of main effect for time, arm, moderator variable, time x arm, time x moderator, arm x moderator, and time x arm x moderator ***interaction term*** in the model (HT-3). The three-way interaction term tests for differential intervention effectiveness in subgroups identified by the moderator variable. Due to the exploratory nature of these analyses, we do not plan to adjust for multiple comparisons in moderator analyses using the subgroups defined above. However, interpretation of results will include reporting on all subgroup analyses and take into account the number of subgroup analyses performed (HT-4).

Patient cost/time and practice resource/time data analysis. The following analyses will be conducted by [name]. Patient cost/time and practice resource and staff time use data will be examined using simple descriptive measures, including minimum and maximum values (range) and means. Descriptive measures will be calculated for practices in each arm of the study as well as for each type of practice and by level of patient participation. To examine the extent to

PRINCIPAL INVESTIGATOR (LAST, FIRST, MIDDLE): [name]

which practice resources are related to patient participation in SMAs, we will examine multiple values calculated for each measure, including a practice-level value, per-patient that agrees to complete these measures, and the value of the measure per-patient that completes different numbers of sessions. Outlier values of these measures will be confirmed with practices prior to the final analysis of these measures. Results from the analysis of practice resources and staff time use will not involve formal statistical tests of differences, as these data will be used for descriptive rather than comparative purposes.

C4.4.2d.2 Qualitative Analysis

To answer the qualitative research questions (QRQ 1-5, Section C.3), a qualitative analysis of practice and patient interview data will be conducted under the direction of [name] with assistance from qualitative PRAs (team of 2-3) and with ongoing input and direction from the core study team. Interview data will be transcribed, cleaned and entered in the ATLAS.ti qualitative software program. Qualitative analysis proceeds as a small group process to capitalize on the triangulation of the data across analysts, resulting in a rich result, accurate to the data. For all analyses, we will begin with a grounded hermeneutic editing approach to the data.¹¹⁰ This approach will help to identify themes that are “grounded” or developed from an interpretation of the data. The analyst team will read through 5 to 10 interviews and together discuss and determine the key themes and the associated definitions and labels (“codes”). These codes will be vetted with the study team and stakeholder representatives. After initial codes are established, the analysts will code – first together, then independently – the data using a coding and editing approach as outlined by Addison, and will compare and reconcile coding until achieving a high degree ($\geq 80\%$) of conceptual inter-rater reliability. The text will be sectioned into segments representing categories of responses.

To answer QRQ 1-3 (patient experience, effects on self-management, and engagement), data from the patient interviews and program observation field note data will be used in the qualitative analytic approach noted directly above, with focus on the grounded theory analysis. To analyze the patient data, codes will be created and utilized to interpret the patient data. Within ATLAS.ti, patient interviews will be grouped into two families: standardized SMA and patient-driven SMA participants. We will examine the codes across these two groups by comparison of quotation reports completed by group to determine if patients in the two SMA conditions express different SMA experiences and changes in self-management behaviors. *A priori* coding using a template framework will be used in both groups to identify evidence of self-determination theory (SDT) constructs. A specific set of codes (i.e., competence, autonomy, relatedness) will be used to gather evidence to support or refute patient expression of SDT constructs interacting with the intervention. Finally, examination of patient expressions of reasons for participation (or non-participation) will be examined with data regarding actual participation to corroborate and explain quantitative results. The final phase consists of preparing interpretive summaries detailing the findings of prior phases. All phases of data processing and analysis will be cross-checked to ensure consistency in application of coding and classification procedures.

The analysis of QRQ-4 (practice sustainability) and QRQ-5 (practice value) will proceed in two directions: 1) Develop overarching themes across all practices; 2) identify factors (practice context, type, intervention arm) that explain perceived value and sustainability of SMAs. Using the approach described above, overarching themes related to the data emerge to describe the experience of the practice members as they interact with the intervention. This analysis will discover if there are key underlying characteristics of the providers or practices such as belief systems or mindsets, or if there are practical reasons that make SMAs work or not work and to what extent. Ongoing meetings will be held with the overall team considering existing literature and associated experiences such that corroborating/legitimizing will occur to seek out additional data to confirm or refute insights from the analysis. After initial analysis has identified data to support one theme or interpretation, particular effort will be devoted to finding negative or disconfirming evidence. Practice members from practices for each type (FQHC, private) will be selected for checking and revision of the thematic groupings prior to final coding.

Second, a matrix approach will be used to examine specific identified factors across practice “cases” to identify if there is a pattern of configurations that may explain results. Each practice will be represented as a case (row in the matrix) and the conditions of interest (practice types and context and intervention characteristics) will form the

PRINCIPAL INVESTIGATOR (LAST, FIRST, MIDDLE): [name]

columns. These configurations of conditions with overall perceived value will be compared using qualitative methods and the formal technique of qualitative comparative analysis.¹¹¹⁻¹¹³ This analysis will help identify factors important to the relative effectiveness of SMAs across model types (standard or patient-driven) and practice characteristics. [name] has experience with this approach and has used it in previous studies.¹¹⁴

Reporting plan (IR-6). The fidelity and participation checklists will capture differential participation, which may influence the effectiveness of the comparators. Progress reports will detail recruitment, enrollment, completeness of follow-up by intervention arm, internal consistency of measures, primary analysis of all outcomes, and any exploratory analyses. For manuscripts, practice and patient recruitment and retention will be tracked and reported in accordance with the CONSORT statement for cluster randomized trials and the RE-AIM extended CONSORT diagram.^{115,116}

D. Patient Population and Subgroups (RQ-3 and RQ-4)

Up to 1000 patients (45.5 patients/practice * 22 practices) will be enrolled in either standardized or patient-driven SMAs and will contribute data to the evaluation. Inclusion criteria for patients include adults at least 18 years old with Type II diabetes, and who receive care in participating practices. Exclusion criteria include pregnancy or plans to become pregnant in the next six months, limited cognitive capacity such as that due to dementia or a developmental disorder, less than one year life expectancy, or plans to leave the area in the next year. These criteria will be finalized with the stakeholders. Subgroups include patients with comorbid mental illness (e.g., depression, anxiety, bipolar disorder). We anticipate each practice will need to invite at least 150 patients to participate in SMAs in order to successfully enroll 46 patients who agree to participate (50% treatment acceptance rate) and retain at least 36 patients who contribute complete data to the evaluation (15-20% attrition). Barriers to enrollment will be addressed as part of stakeholder meetings throughout the implementation period (see engagement plan). Practices will use their usual procedures to maximize patient attendance at visits, including calling patients to remind them of upcoming visits, arranging for transportation (often needed for patients in FQHCs), and calling patients who do not show for a scheduled visit to assess barriers to and encourage future attendance (PC-2, retention). We will also attempt to collect all follow-up survey data from patients who discontinue participation, through email or telephone.

Table 5. Recruitment Plan for Prospective Studies:

| | |
|--|--|
| Estimated number of potentially eligible study participants (describe how this number was determined [e.g., EHR, claims data, clinic logs, administrative data, other]): | Participating practices see on average ~500 unique adult patients/year with diabetes (estimated from EHR data) |
| Total number of study participants expected to be screened: | N/A (screening does not apply) |
| Total number of study participants expected to be eligible of those screened: | N/A |
| Target sample size (use same number stated in milestones): | 1000 patients (45.5/practice *22 practices) |
| If applicable, total number of practices/centers that will enroll participants: | 22 |
| Projected month first participant enrolled (month after project initiation): | Month 9 (pilot cohort) |
| Projected month last participant enrolled (month after project initiation): | Month 45 |
| Projected rate of enrollment (anticipated number enrolled per month of enrollment period): | 1 new cohort of 8-10 patients per practice every 3 months |
| Estimated percentage of participant dropout: | 15-20% |

E. Investigators and Environment (Criterion 4)

As noted above, this study will take place in the CU-SOM's ACCORDS in collaboration with member practices of the SNOCAP PBRNs. The research team has considerable expertise and experience in practice-based research, diabetes self-management interventions, study design and analysis, implementation science, stakeholder engagement, mental and behavioral health, and mixed methods research. [name], the PI, is a social health psychologist and health services researcher with experience in mixed methods research and application of psychological theory to the design and testing of interventions for chronic disease management in primary care settings. She is the Associate Director of SAFTINet, a distributed data network and SNOCAP-affiliated PBRN with infrastructure linking clinical, claims and patient-reported data. With the support of the Co-PI and Co-investigators, with whom she has a track record of successful collaboration, she is well-prepared to lead this study. [name], the Co-PI, is a clinical psychologist and director of research and evaluation at the Jefferson Center for Mental Health with a history of successful collaboration with the clinics engaged in this study. She has extensive experience in stakeholder engagement, mental health and primary care, and leading implementation of similar chronic disease management programs.

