C.4.1 Study Design. This is a pragmatic, cluster randomized comparative effectiveness trial. Given the complexity of systems and processes needed to implement SMAs, and the possibility of contamination effects, randomization will be clustered at the practice level using covariate constrained randomization.⁵⁵⁻⁵⁷ Twenty-two practices will be randomly assigned to either standardized or patient-driven diabetes SMAs (10 per condition). During the 24-month implementation period, each practice will conduct SMAs with around 8 cohorts of 8 to 10 patients each (ultimately yielding up to 72 patients per practice). The initial plan is that cohorts of adult patients with T2DM will progress through 6 weekly SMA sessions, and a new cohort will begin every 3 months, but practices can choose their own timeline. A mixed-methods evaluation will include quantitative (practice and patient-level surveys, electronic health records (EHR), and participation and intervention fidelity tracking data) and qualitative (practice and patient interviews, observation) components.

Sample Size and Power Calculations: Previous power calculations used 1,440 total patients, which is not feasible given recruitment challenges by practices. We are expecting N (total) = 22 clinics, 1,000 patients (11 clinics and 500 patients

PRINCIPAL INVESTIGATOR (LAST, FIRST, MIDDLE): [name]

per condition), allowing for ~15-20% attrition (leaving 400 patients per arm). However, we are estimating power based on 20 practices and provide a possible range of potential power to detect main effects. We estimated the minimum effect sizes detectable for different power calculations for various numbers of practices and patient sample sizes and intraclass correlations (ICC; see table below), with effect sizes of approximately .29 to .35 for intent-to-treat analyses of primary outcomes with a type-1 error rate of .05. Power for planned subgroup analyses for patient characteristics (e.g., mental illness, health literacy) is also shown. An effective sample size of 67 per group is required to detect a medium linear trend effect between groups (increasing from 0 to .5SD) using general linear mixed models with random slopes and intercepts.⁵⁸

| Practices per arm: N | Patients per practice: N | With 15-20% attrition: N | ICC | Effective sample size | Detectable difference (effect size) | Power |

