|---|--------------------------|--------------------------|-----|-----------------------|-------------------------------------|-------|
| 10 | 53.4 (534 per arm) | 44.5 (445 per arm) | 3% | 193 | .29 | >80% |
| 10 | 53.4 (534 per arm) | 44.5 (445 per arm) | 5% | 140 | .34 | >80% |
| 10 | 46.2 (462 per arm) | 38.5 (385 per arm) | 3% | 181 | .30 | >80% |
| 10 | 46.2 (462 per arm) | 38.25 (385 per arm) | 5% | 134 | .35 | >80% |
| For subgroup analyses (for patient characteristics) | | | | | | |
| 10 | 11.5 (115 per arm) | 9.6 (96 per arm) | 3% | 76 | .46 | >80% |
| 10 | 11.5 (115 per arm) | 9.6 (96 per arm) | 5% | 67 | .49 | >80% |

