randomization procedure.⁸⁸ **Covariates (to adjust for potential confounding) and potential moderators will include the following:** mode of delivery of SMA (in-person vs. telehealth), age, gender, race/ethnicity, comorbidity index, insulin dependence, baseline diabetes distress, health literacy, and mental illness. Recent literature on cluster randomized trials notes that imbalance in covariates is more of a problem than for individually randomized trials, and covariates should be included to improve precision and should be selected prior to analysis.^{55,88,89} In the event normality assumptions are not met, we will use transformations to normalize distributions, ordinal or Poisson regression where appropriate, and/or the appropriate link function (e.g. logit link for dichotomized measures).⁹⁰⁻⁹² We will employ intent to treat analyses using general (generalized) linear mixed models (GLMMs) to incorporate data structures that are both hierarchical and longitudinal.^{91,93-97} Hypothesis tests will be two-sided with $\alpha = .05$ or p values reported. Goodness of fit statistics and model fitting diagnostics will be used to assess for influential points, outliers, overdispersion and heteroscedasticity and to evaluate alternative model specifications.⁹⁰ All statistical analyses will be performed using SAS version 9.4 (SAS Institute Inc., Cary, N.C.).

Missing Data (MD-2). Prior to beginning analyses described below to address study hypotheses, we will examine the data carefully to determine whether patterns of missing are ignorable (MCAR or MAR) or non-ignorable (MNAR).⁹⁸⁻¹⁰¹ If so, we will employ likelihood-based methods that utilize all available data (MD-4), adjusting for covariates that are associated with missingness (MD-3). If missingness is non-ignorable we will employ pattern mixture models.¹⁰² Sensitivity analyses will be carried out using multiple imputation approaches (MD-5).

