Heterogeneity of treatment effects (HTE) (HT-2). It is not known at this time whether patient-driven SMAs will benefit certain patients more than others. Thus, in addition to the analyses described above, we will conduct exploratory analyses to test for potential effect modification (moderator of intervention effectiveness) by selected patient characteristics (HT-1). While this study may be powered to detect effect modification with large effect sizes, the planned sample size of 1000 enrolled will allow only for testing effect modification of patient characteristics representing subgroups of an average of 10 patients per practice with that characteristic. For example, to do a subgroup analysis of patients with mental illness, we would need an average of 10 patients with mental illness per practice to test this effect. This analysis is described just above for analysis of hypothesis IV with mental illness as a potential moderator; mental illness comorbidity is our primary target for HTE analyses and will be examined for every hypothesis above. Additional sub-populations of interest are defined by gender, Hispanic ethnicity, and health literacy; existing evidence suggests possible differential participation and effectiveness for these groups.^{29,108,109} The general hypothesis for these moderator analyses is as follows: The effects of the patient-driven vs standardized SMAs on diabetes distress (and other primary and secondary outcomes) will differ for patients with mental illness compared to patients without mental illness (male vs. female, Hispanic ethnicity vs not, high vs. low health literacy, food security, cohort conducted in English or Spanish, virtual vs. in-person, insulin dependence). To assess for possible heterogeneity of treatment effects by mode of delivery (effect modification, moderator) additional analyses will be performed including the appropriate two and three-way interactions between treatment arm and mode: arm x modality interaction for single outcomes, arm x time x modality along with relevant two-way interactions for longitudinal analyses. Additionally, sensitivity analyses will be performed to further explore delivery mode. Additionally, we will examine variability between SMA groups separately for standard and patient-driven arms to determine if the group itself (especially in the patient-driven arm) is an important contributor to differences in outcomes.

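### The two subgroup power rows describe an arm comparison inside one subgroup, while the planned moderator analyses test an interaction, for which no power is stated

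*Combined protocol and SAP*

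**What the plan says.** Section C.4.1 introduces the rows with "Power for planned subgroup analyses for patient characteristics (e.g., mental illness, health literacy) is also shown". They read "10 | 11.5 (115 per arm) | 9.6 (96 per arm) | 3% | 76 | .46 | >80" and "10 | 11.5 (115 per arm) | 9.6 (96 per arm) | 5% | 67 | .49 | >80" (percent). The columns are practices per arm, patients per practice before and after attrition, ICC, effective sample size, detectable effect and power.

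Section C4.4.2d.1 defines the moderator analyses. For Hypotheses I, II and IV, "The three-way interaction term tests for differential intervention effectiveness in subgroups identified by the moderator variable". For Hypothesis III the term is arm by mental illness. The paragraph on heterogeneity of treatment effects makes mental illness the main target, to be examined under every hypothesis. It calls these analyses exploratory and suggests that only large effect modification may be detectable. On subgroup size it says "we would need an average of 10 patients with mental illness per practice to test this effect".

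**The concern.** A comparison of the arms within a subgroup asks whether the patient-driven model works better there. An interaction asks whether its advantage there differs from its advantage elsewhere, and that difference is usually smaller than the subgroup's own effect. The table's power is offered for the planned subgroup analyses, but it belongs to a test the plan does not describe.

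The trial sets out to learn for which patients the patient-driven model is better. Someone who reads a null interaction by mental illness against a printed power above 80% could take it as good evidence of equal benefit. Under effects consistent with the plan's own average, it might be weak evidence.

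**Working it through.** **Inputs.** Significance level: C.4.1, "with a type-1 error rate of .05". Sidedness: C4.4.2d.1, "Hypothesis tests will be two-sided with" alpha .05. Subgroup: 96 completers per arm, 9.6 per practice. Whole arm: 385 completers, from "10 | 46.2 (462 per arm) | 38.5 (385 per arm) | 3% | 181 | .30 | >80" (percent). Overall effect: 0.30, from the effect-size paragraph of C.4.1. The subgroup share is therefore 96/385 = 24.9%. The documents give no prevalence of mental illness, so this share is an assumption taken from the table.

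**Step 1: reproduce the rows.** Effective n = 96/[1 + (9.6 − 1) × ICC].
- ICC 3%: 96/1.258 = 76.3 (printed 76). Detectable effect 2.8016 × √(2/76.3) = .454 (printed .46).
- ICC 5%: 96/1.43 = 67.1 (printed 67). Detectable effect 2.8016 × √(2/67.1) = .484 (printed .49).

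Power at the printed effects is 81% in both rows. The other 289 patients per arm do not enter, so the rows are a comparison of the arms within the subgroup.

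**Step 2: the interaction implied by those effects.** With subgroup effect d and overall effect 0.30, the effect in the others is [0.30 − (96/385)d]/(289/385).
- d = .46: .247 in the others, interaction .213.
- d = .49: .237 in the others, interaction .253.

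**Step 3: power on the table's scale.** The practice effect is shared by subgroup and non-subgroup patients of the same practice, so it cancels. SE = √[2(1 − ICC)(1/96 + 1/289)] = .164 (ICC 3%) or .162 (ICC 5%). Power = Φ(interaction/SE − 1.96) = **25%** or **34%**. A 4,000-replicate simulation with 20 practices gave 25.1% and 34.9%. With 400 completers per arm the results are 25.2% and 34.1%; with 445 they are 24.5% and 33.2%.

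**Step 4: sensitivity.**

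| Assumption | ICC 3% | ICC 5% |
|---|---|---|
| Change-score variance 2(1 − ρ) per patient, ρ = .3 | 19% | 25% |
| ρ = .5 | 25% | 33% |
| ρ = .7 | 38% | 50% |
| ρ = .8 | 53% | 67% |
| Independent design effects for subgroup and others | 19% | 22% |

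The ρ rows are needed because the three-way term under Hypothesis I is a contrast of changes, and the documents give no pre-post correlation. Step 3 corresponds to ρ near .5.

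**Step 5: what would give 80% power.** The smallest detectable interaction is 2.8016 × .164 = .46 SD (ICC 3%) or 2.8016 × .162 = .45 SD (ICC 5%). With an overall 0.30, the subgroup effect must be 0.30 + (289/385) × .46 = .645, or about .64 at ICC 5%. An interaction that is itself .46 or .49 has 80% or 86% power with the practice effect cancelling, and 65% or 62% with independent design effects.

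**Step 6: other splits, same formula and overall 0.30.**
- Even split (Table 6 projects 500 men and 500 women): effect in the others .14 or .11, interaction .32 or .38, SE .142 or .141, power 62% or 77%. Smallest detectable interaction about .40 or .39 SD.
- Ethnicity at 58/42: 48% or 63% if the 42% group has the larger effect, 75% or 89% if the 58% group does.

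**The case against.** The strongest reply is that .46 SD is also, to rounding, the smallest interaction detectable for a 25% moderator. Read as sizes of effect modification, the rows roughly hold, and such an interaction is compatible with an overall 0.30 (about .645 inside the subgroup and .185 outside). That stands as arithmetic, so the rows contain no calculation error. But the match depends on the practice effect cancelling. The rows' effective sample size is that of the subgroup alone, and nothing labels .46 or .49 as an interaction.

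The plan also discloses much of the limitation. It calls these analyses exploratory, speaks only of large effects, and undertakes to report all subgroup analyses and to weigh how many were done. This lowers the weight of the point without correcting the table: C.4.1 itself calls a difference growing to .5 SD medium, so the printed .46 and .49 are not large in the plan's own terms.

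A reader might infer that the plan declares 10 patients per practice to be enough. The wording does not support that; it states a number needed, which reads as a minimum. Nor does any section say that a null interaction will be taken as equal effectiveness. That risk lies in how the table could be read.

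**Conclusion.** The point holds as a mismatch between the stated power and the planned test. The power above 80% is for the arm comparison within a subgroup, the plan tests interactions, and no interaction power is stated.

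The 25% and 34% are conditional. They require .46 or .49 to be the subgroup's own effect, an overall effect of 0.30, a patient-level moderator with a share near 25%, follow-up-SD units, a practice effect that cancels, and no practice-by-moderator variance. A reader might infer that all the moderator tests have 25–34% power, or that they would miss such effects about two times in three. The documents do not support that for gender or ethnicity, whose projected splits give much higher power. The figures also do not cover moderators set at cohort level, such as language and delivery mode. Hypothesis III has the same mismatch through its two-way term, but its outcomes are acceptance and attendance, so these SD-unit figures do not transfer directly.

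No primary analysis or sample size depends on the point. It is worth correcting because mental illness is the leading heterogeneity question.

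**What to change.** In the C.4.1 table, relabel the two rows as an arm comparison within the subgroup, not the planned interaction test. Beside them, give the smallest interaction detectable with 80% power: about .46 SD for a patient-level moderator held by 25% of patients, and about .40 SD for an even split. State the assumptions: follow-up-SD units, practice effect cancelling, no practice-by-moderator variance. Add the range over the pre-post correlation; for the 25% moderator it runs from about .55 SD at ρ = .3 (2.8016 × .197) to about .30 SD at ρ = .8 (2.8016 × .105). Say that cohort-level moderators are not covered.

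In the heterogeneity paragraph of C4.4.2d.1, keep the exploratory and large-effect caveats. Tie the figure of 10 patients per practice to the detectable interaction of about .46 SD, rather than leaving it as what is needed to test the effect. Add that moderator results will be reported as interaction estimates with 95% confidence intervals, and that a non-significant interaction will not be read as equal effectiveness.

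The cost is wording and a few table entries, with no new patients or data. The stated subgroup power will look less favourable.

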Hypothesized Effect Size for Comparative Effectiveness for Main Patient-Centered Outcome: The hypothesized effect size for comparative effectiveness of patient-driven versus standardized SMAs is **0.30** (a small to medium effect), based on an expected **difference in change in HbA1c of 0.60%** between arms and a SD of 2.0⁵⁹ for follow-up HbA1c. Meta-analysis shows the average effect of SMAs on HbA1c is -0.55%.⁶ This is the expected effect of the standardized SMAs in this project. A study of a similar patient-driven SMA model to that proposed for this project led to an average change in HbA1c of -1.15%.³⁰ This is the expected effect of patient-driven SMAs in this project. For instance, assuming an average baseline HbA1c of 9% (SD 1.2), the patient-driven model is expected to yield a follow-up HbA1c of 7.85%, and the standardized model is expected to yield a follow-up HbA1c of 8.45%. The increased effect of patient-driven SMAs could be attributed to greater patient engagement in treatment and better understanding and uptake of diabetes self-care behaviors, in accordance with the intervention conceptual model. Thus, a 0.60% difference in change in HbA1c between standardized and patient-driven SMAs is supported by both theory and evidence. Furthermore, an effect size smaller than 0.30 would not be clinically significant, and any increased practice burden of patient-driven SMAs would likely be unjustifiable. **Diabetes distress is the main patient-centered outcome**, but data are not directly available for distress, so we extrapolate from evidence on HbA1c. Evidence shows that a 0.5 SD change in HbA1c corresponds to a 1-unit change on the diabetes distress measure we intend to use.^{60,61} A 0.60% difference in change in HbA1c would correspond to a 1.20 unit difference in DDS-17 change scores between arms. The patient-driven model may have even stronger effects on distress than on HbA1c. Allowing patients to choose session topics could help them focus on the areas where they need the most help, such as fostering family support, decreasing the sense of being overwhelmed by diabetes.

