As shown above in Section C.4.1, the sample size needed to detect the hypothesized effect size is 20 practices with 60 patients each. Assuming 20% loss to follow-up among participants, each practice will be asked to enroll at least 72 patients each. Enrollment and data collection will continue until achieving complete data for at least 60 patients/practice; practices may enroll more than the minimum. Recruitment strategies will be determined as part of Aim 1. Strategies may include identifying patients in existing diabetes registries, systematic screening and referral for new diagnosis of T2DM, and/or through provider referral. While strategies may vary somewhat across practices, the objective is to enroll as large and representative sample of eligible patients as possible in that practice. *Patients will be enrolled in SMAs as part of their regular health care; at the practice level, this is considered quality improvement (QI) and similar projects have been approved as such by our Institutional Review Board.* All survey data collected from patients will be collected as part of the SMA process, as described below, and will be made available to inform clinical decision-making, such as which SMA topics to prioritize and to provide feedback to patients on their progress; use for research purposes will thus be considered secondary analysis. In our experience, making survey data relevant to clinical care is

PRINCIPAL INVESTIGATOR (LAST, FIRST, MIDDLE): [name]

the best way to ensure the data are collected systematically.³⁷ A subset of SMA patients will be recruited to participate in qualitative interviews and patient out of pocket cost and time commitment surveys for explanatory purposes. A description of this sampling plan is described in Section C.4.4.2c, Data Collection (Qualitative). Protocols to ensure data are collected thoroughly and systematically will be at the practice level, managed on a daily basis by the local site SMA coordinator and jointly overseen by the implementation and research project managers. Practices engage patients in treatment as they do in real-world care (i.e., not for research purposes), using reminder and follow-up calls to encourage patient attendance at visits, so that the findings of this research will be directly applicable to other practice settings.

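### Section C.4.4.2a still sets a requirement and an enrol-until rule (20 practices × 60 complete patients) that C.4.1 does not show and the planned 1,000 patients cannot meet; the invitation sum in Section D also fails

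*Combined protocol and SAP*

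**What the plan says.** **C.4.4.2a, Recruitment and Retention.** Citing C.4.1, it says that "the sample size needed to detect the hypothesized effect size is 20 practices with 60 patients each". Allowing for 20% loss, it adds that "each practice will be asked to enroll at least 72 patients each". Its closing rule is "Enrollment and data collection will continue until achieving complete data for at least 60 patients/practice".

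**C.4.1, Sample Size and Power Calculations.** "Previous power calculations used 1,440 total patients, which is not feasible given recruitment challenges by practices". The section now expects 22 clinics and 1,000 patients (11 clinics and 500 patients per arm), with 400 per arm left after 15-20% attrition. Power is worked out for 20 practices. The main-effect rows of the table use 44.5 or 38.5 completers per practice (one entry is printed as 38.25). One row reads "38.5 (385 per arm) | 3% | 181 | .30 | >80" (the last entry is a percentage).

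**C.4.1, Study Design.** "Twenty-two practices will be randomly assigned to either standardized or patient-driven diabetes SMAs (10 per condition"). The same paragraph gives a yield of at most 72 patients per practice from about eight cohorts.

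**Section D and Table 5.** Up to 1,000 patients are to be enrolled, as 45.5 × 22. Each practice invites at least 150 in order to enrol 46, at 50% acceptance, and keeps at least 36 with complete data.

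**Elsewhere.** Aims 1c and 2 (C.1), C.4.3.1c and the patient-interview paragraph of C.4.4.2c say 20 practices. Aim 2 and the Protection of Human Subjects section still carry 1,440 patients.

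**The concern.** C.4.4.2a presents a sample-size requirement as something already shown in C.4.1, and a reader who turns to C.4.1 does not find it. The requirement matches the design that C.4.1 sets aside, since 20 × 72 = 1,440.

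This matters because C.4.4.2a holds the only rule that ties the end of trial enrolment to a patient count. One section asks a practice for at least 72 patients and another plans for about 46. Whether the trial reached its planned size would depend on which section is read. Section D has a similar fault: its invitations, acceptance rate and enrolment cannot all be right together.

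**Working it through.** **1. Reproduce C.4.1 first.** Inputs from C.4.1 and the analytic plan: 10 practices per arm, two-sided alpha .05, ICC 3% or 5%. The effective n per arm is k·m / (1 + (m − 1)·ICC). The difference detectable at 80% power is (1.960 + 0.842)·√(2 / effective n).

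| Completers per practice | ICC | Effective n: table / recomputed | Detectable: table / recomputed |
|---|---|---|---|
| 44.5 | 3% | 193 / 193.1 | .29 / .285 |
| 44.5 | 5% | 140 / 140.2 | .34 / .335 |
| 38.5 | 3% | 181 / 181.2 | .30 / .294 |
| 38.5 | 5% | 134 / 133.9 | .35 / .342 |

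The table's differences are at or slightly above the 80% values, so its entries of more than 80% hold.

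**2. Look for 60 per practice.** No row or sentence in C.4.1 contains it. For the hypothesised 0.30 at 80% power the effective n needed is 175 per arm. The completers needed per practice are then m = 175(1 − ICC) / (10 − 175·ICC):
- ICC 3%: 169.75 / 4.75 = 35.7.
- ICC 5%: 166.25 / 1.25 = 133.
- m = 60 corresponds to an ICC of (600/175 − 1)/59 = 4.1%, which C.4.1 does not tabulate.

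**3. Test the enrol-until rule against the plan.**
- Complete patients required: 20 × 60 = 1,200, or 22 × 60 = 1,320.
- Enrolment planned: 22 × 45.5 = 1,001, stated as up to 1,000.
- Complete patients expected: 500 × 0.8 = 400 per arm, or 800 in all. Section D's minimum gives 22 × 36 = 792.
- With no loss at all, 1,000 is still below 1,200.

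**4. Check the allowance for loss in C.4.4.2a.** 72 × 0.8 = 57.6, not 60; a true 20% loss would need 60 / 0.8 = 75. The 72 is 60 × 1.2. The C.4.1 table uses the same multiplier (44.5 × 1.2 = 53.4; 38.5 × 1.2 = 46.2), which corresponds to a loss of 1 − 1/1.2 = 16.7%. C.4.1's Study Design paragraph treats 72 as the most a practice will yield, whereas C.4.4.2a makes it the least.

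**5. Check the invitations in Section D.** 150 × 0.50 = 75. To enrol 46 takes 46 / 0.50 = 92 invitations, or acceptance of 46 / 150 = 30.7% from 150. Since 150 × 0.50 × 0.80 = 60, the 150 may be left over from the old target; that is an inference.

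**The case against.** C.4.1 tells the reader plainly that the 1,440 basis has been given up, so C.4.4.2a can be read as a known leftover. Enrolment is also bounded in time, by a 24-month implementation period and a last enrolment at month 45. Practices are to work from a manual and worksheet, and the worksheet outline in Appendix B contains neither 60 nor 72. The limit of 1,440 in the human-subjects section is a ceiling that 1,000 does not breach. All of this is fair, and it makes actual over-enrolment less likely. It does not repair a rule that stands in current text and contradicts the stated total.

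On the allowance for loss, multiplying by 1.2 is the plan's consistent convention, and 16.7% lies inside its 15-20% range. What remains is that C.4.4.2a labels the loss 20%.

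Two stronger readings are tempting and are not supported:

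- A reader might infer that C.4.1's method could never have produced 60. It could, at an ICC near 4%. The supportable statement is that C.4.1 shows no such requirement, and that neither tabulated ICC leads to 60.
- A reader might set the row "44.5 (445 per arm) | 5% | 140 | .34 | >80" beside the remark that "an effect size smaller than 0.30 would not be clinically significant" and conclude that the power claim is wrong or that more patients are needed. The stated power belongs to the difference in the same row (.34), not to 0.30. The table shows openly that at ICC 5% the detectable difference is .34 to .35. There is no error there to correct.

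**Conclusion.** The point holds as an internal contradiction. The requirement and the enrol-until rule in C.4.4.2a belong to a superseded design. They exceed planned enrolment by at least 200 complete patients (1,200 against 1,000), and by 320 if all 22 practices are held to 60. Against the roughly 800 completers expected, the gaps are about 400 and 520. Section D's invitation figures disagree by 29 patients per practice (75 against 46).

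These results are simple products of the plan's own figures. The only assumption is that C.4.1, Section D and Table 5 state the current plan. C.4.1's withdrawal of 1,440 and the 1,000 repeated in the heterogeneity paragraph of the analytic plan both support that. Nothing here shows that the power table is wrong or that the planned size is inadequate.

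**What to change.** - **C.4.4.2a:** delete the 20 × 60 statement, the request for at least 72 and the enrol-until-60 rule. Put in the current target: 22 practices (11 per arm), up to 1,000 enrolled (about 46 per practice), and about 36 per practice or 400 per arm complete at 20% attrition. If a continue-until rule is still wanted, state it against that target.
- **Section D:** make the invitations, acceptance rate and enrolment agree, and state which acceptance rate is assumed.
- **C.4.1, Study Design:** reconcile the 10 practices per arm with 22 practices, and the yield of up to 72 per practice with about 46.
- **Aims 1c and 2, C.4.3.1c and the patient-interview paragraph:** align the practice count.
- **Aim 2 and Protection of Human Subjects:** align the 1,440.

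The cost is text editing only. The power table can stay as it is, and neither the design nor the number of patients changes.
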